As noted above, after enrollment was complete, but before the randomization, the protocol was amended because 13% (155 of 1165) of enrolled participants received primary care at 111 clinics that each served ≤ 2 enrolled participants. Because it was beyond the scope of the project to provide AD to so many clinics, prior to randomization, the decision was made and approved by the sponsor to include these 155 enrolled participants in a second cohort in a stratified randomization, such that Cohort 1 (AD-eligible) comprised participants seen in primary care clinics serving ≥ 3 enrolled participants described above. Cohort 2 (AD-ineligible) comprised participants whose primary care clinic served ≤ 2 enrolled participants who were randomized to CHW or TAU in a 1:1 ratio.

The patient population will consist of approximately 1300 adult outpatient smokers with SMI who receive psychiatric rehabilitation services through CBFS and ACT programs at Bay Cove Human Services and Vinfen Corporation. This includes adults primarily with schizophrenia spectrum disorders and bipolar disorder.

Inclusion/exclusion criteria:

Primary care clinics/physicians/nurses/care team: There are no requirements for clinics to be included or excluded except that they provide medical care to people with SMI who smoke and who are served by the CBFS and ACT psychiatric rehabilitation systems of Bay Cove and Vinfen. There are no exclusion criteria for prescribers related to specialty (e.g. internal medicine, psychiatry, pulmonary medicine, family medicine, clinical nurse specialist), experience with smoking cessation therapies, or experience working with people with SMI.

Since the patient and their prescriber will decide together on the timing of initiation of any pharmacotherapeutic cessation aid, there will be no exclusion criteria for patients due to medical illness or psychiatric symptom severity or stability or substance use.

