4.5 Mixed Methods Research Questions

MRQ 1a. Among patient participant, CHW and primary care provider (PCP) stakeholders, what are the barriers and facilitators to use of the intervention and how do these compare according to performance level, namely, patient quitters, PCP prescribers, and CHW facilitators?

MRQ 1b. Among patient participant, PCP, and CHW stakeholders, what are the barriers and facilitators to use of the intervention and how do these compare according to level of engagement?

MRQ 2a. How do the PCPs, grouped by primary care clinic, differ by performance level and how do their experiences with the intervention, and the barriers and facilitators compare across these groups?

MRQ 2b. What is the association between engagement with the AD intervention among high or low performers, and how did barriers and facilitators experience compare across these groups?

QQ (Qualitative Question) 3. What barriers and facilitators do stakeholders, such as clinical, payor and policy leaders anticipate impacting the implementation of the integrated smoking cessation treatment?

Time and Events Table

VII. BIOSTATISTICAL ANALYSIS

1. Analytic Plan.

With the original 3-arm design, 1/3 of clinics that serve 3 or more smokers with SMI will be randomly assigned to the TAU arm and 2/3 will be assigned to receive AD. At the clinics assigned to AD, half of the smokers with CBFS or ACT services who participated in the baseline assessment will be randomly assigned to be offered CHW support to quit smoking. The primary outcome measure will be the difference in smoking rates and self-reported overall health from year 1 to year 3 between those assigned to AD+CHW compared to TAU. In secondary analyses, we will also compare these outcomes in the AD+CHW group compared to the AD group, and in

Year	1	R	2	3
Study Visit	1	A	2	3
Questions		N		
Demographics (age, sex, race, living situation)	X	D		
Smoking Status	X	O	X	X
Heaviness of Smoking Index (HSI)	X	M	X	X
Smoking questionnaire	X	I	X	X
Single item Health related quality of life (SF-1)	X	Z	X	X
		A		
		T		
Biomeasure		I	X	X
Exhaled CO (in those who report being non-smokers)	X	O		
Quantitative Data Collection				X
Payment	\$5	N	\$5	\$5

AD compared to TAU. For participants who receive primary care from a clinic that serves two or fewer adult smokers with SMI, we will randomize half to receive CHW services. This comparison can be kept entirely separate from the main analysis of AD vs AD+CHW vs TAU

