To include participants from Cohort 2, we conducted a secondary, factorial analysis of the impact of the two interventions and their combination, using cohort as a factor, that was planned when we randomized participants whose clinics cared for ≤ 2 participants.

To determine the influence of the assigned intervention mediated via its impact on TUD medication use, and varenicline use specifically, the unmediated impact of the study interventions on abstinence, and the impact of TUD medication use and varenicline use specifically on abstinence we conducted mediation analyses using the combined cohorts. We assessed associations between intervention assignment, TUD medication use, and year-2 abstinence via path analyses based on logistic regression. Separate analyses assessed the impact of taking any TUD medication and varenicline specifically. Estimates of the indirect effect were computed per each imputation run and pooled using Rubin's method.

2. Statistical methods.

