Aim 1. Hypothesis 1a. *Those who receive AD+CHW will demonstrate higher rates of biochemically verified tobacco abstinence than those who receive usual care (TAU).* The primary outcome will be the proportion of smokers who are abstinent at their Year Three Assessment. This will be 12-24 months after randomization to study interventions because assessments are conducted in the pragmatic setting of the annual psychiatric rehabilitation team meetings. This smoking abstinence rate will be compared between the two groups using a generalized linear mixed models logistic regression, with random effect for clinic, assumed to be normally distributed [114]. **Hypothesis 1b.** *Those who receive AD+CHW will demonstrate higher rates of biochemically verified tobacco abstinence than those who receive AD only.* This rate will be compared between the two groups using logistic regression. **Hypothesis 1c.** *Those who receive AD will demonstrate higher rates of biochemically verified tobacco abstinence than those received TAU.* This rate will be compared between the two groups using generalized linear mixed models logistic regression. Hypothesis 1d. Participants assigned to receive CHW will demonstrate a higher rates of biochemically verified, 7-day point-prevalence tobacco abstinence than those assigned to TAU at the Year 3 Assessment. This will be tested with factorial analysis in the combined sample, using cohort as a factor. Additionally, we will compare MassHealth pharmacy claims data for smoking cessation medications (varenicline, bupropion and nicotine replacement therapy) to examine differences in prescribing patterns of providers randomized to AD compared to those randomized to TAU. We will also examine the effect of the interventions on rates of participants filling prescriptions for smoking cessation medication (i.e. AD, AD+CHW, CHW, TAU)

Aim 2: Hypothesis 2. *Those who receive AD+CHW will demonstrate improved Quality of Life compared to those who receive usual care, as assessed with the SF-1 (Overall Health).* We will assess this hypothesis with a random effects model with baseline, duration of follow up, and treatment group as covariates and a clinic random effect. We will use data from the last visit during the study as the dependent measure.

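### The mediation analyses and the four-arm prescription-fill comparison pool both cohorts with no stated cohort term, although AD could be assigned only in Cohort 1 and CHW alone only in Cohort 2

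*Combined protocol and SAP*

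**What the plan says.** Section III explains why there are two cohorts: "13% (155 of 1165) of enrolled participants received primary care at 111 clinics that each served ≤ 2 enrolled participants". The decision, taken before randomisation, was to "include these 155 enrolled participants in a second cohort in a stratified randomization". The allocation then differs by cohort:

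- Cohort 1 (Section VII.1): "1/3 of clinics that serve 3 or more smokers with SMI will be randomly assigned to the TAU arm and 2/3 will be assigned" to AD. Half of the participants at AD clinics are then offered a CHW.
- Cohort 2 (Section III): "Cohort 2 (AD-ineligible) comprised participants whose primary care clinic served ≤ 2 enrolled participants who were randomized to CHW or TAU in a 1:1 ratio".

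Three planned analyses draw on both cohorts:

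- **Factorial analysis (Hypothesis 1d).** Cohort is named as a factor in Section II, Section VII.1 and Section VII.2.
- **Mediation (Section VII.1).** The text says that "we conducted mediation analyses using the combined cohorts". It describes logistic path models that link assignment, medication use and abstinence, and names no other covariate.
- **Prescription fills (Section VII.2).** "We will also examine the effect of the interventions on rates of participants filling prescriptions for smoking cessation medication (i.e. AD, AD+CHW, CHW, TAU". No model or adjustment is named.

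On the relation of Cohort 2 to the three-arm comparison, Section VII.1 says: "This comparison can be kept entirely separate from the main analysis of AD vs AD+CHW vs TAU".

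Section IV lists the study data sent to MassHealth for the claims linkage: arm, survey dates, age group, gender, race, ethnicity, self-reported medication use and self-reported abstinence. Cohort is not on the list. The returned file carries a new encrypted ID that cannot be tied to the study ID.

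**The concern.** A participant's chance of being in an AD arm is about 2/3 in Cohort 1 and zero in Cohort 2. The chance of CHW without AD is zero in Cohort 1 and one half in Cohort 2. Randomisation therefore balances the arms within a cohort, not across the pooled sample.

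Practices that see one or two enrolled smokers with SMI may prescribe, and their patients may quit, at different rates from practices that see many. In a pooled analysis without cohort, that difference is read partly as an intervention effect. In the mediation analysis it can enter twice: through the path from assignment to medication use, and through the path from medication use to abstinence, because cohort may be related to both.

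What is at stake is the trial's evidence on mechanism, that is, whether the interventions raise use of cessation medication and work through it. For fills there is a further problem. If cohort is not in the linked file, the analyst cannot separate Cohort 1 TAU from Cohort 2 TAU at all.

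**Working it through.** **Inputs**

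- Enrolled 1165, of whom 155 are in Cohort 2 (Section III).
- Cohort 2 split 1:1 between CHW and TAU (Section III).
- Cohort 1 clinics split 1/3 TAU and 2/3 AD, with participants at AD clinics split 1:1 on CHW (Section VII.1).
- Assumption: the participant split in Cohort 1 follows the clinic split.
- d = mean outcome in Cohort 2 minus Cohort 1 under the same treatment. The documents give no value; 3 to 5 percentage points is assumed for illustration.

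**The plan's own figure.** 155/1165 = 13.3%, which agrees with the stated 13%.

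**Expected cell sizes.** Cohort 1 has 1165 - 155 = 1010 participants, so each arm has 1010/3 = 336.7, about 337. Each Cohort 2 arm has 155/2 = 77.5.

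| Arm | Cohort 1 | Cohort 2 | Cohort 2 share |
|---|---|---|---|
| TAU | 336.7 | 77.5 | 77.5/414.2 = 18.7% |
| AD | 336.7 | 0 | 0% |
| AD+CHW | 336.7 | 0 | 0% |
| CHW alone | 0 | 77.5 | 100% |

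**Spurious contrast with no treatment effect.** For an arm-coded comparison without cohort, the error is (Cohort 2 share of the arm - Cohort 2 share of TAU) × d.

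- AD vs TAU, and likewise AD+CHW vs TAU: (0 - 0.187)d = -0.19d. For d of 3 to 5 points this is -0.6 to -0.9 points.
- CHW alone vs TAU: (1 - 0.187)d = +0.81d. For d of 3 to 5 points this is +2.4 to +4.1 points.
- AD vs CHW alone: (0 - 1)d = -d, so this contrast lies wholly between cohorts.

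The signs reverse if d is negative.

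**Sensitivity to the Cohort 1 split.** If TAU holds 30% of Cohort 1 (303), its Cohort 2 share is 77.5/380.5 = 20.4%. If it holds 36% (364), the share is 77.5/441.1 = 17.6%. The CHW-alone multiplier therefore stays between 0.80 and 0.82.

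**After the change.** A weighted least-squares fit to the five cohort-by-arm cells, with AD, CHW and cohort terms and no treatment effect, returns zero for AD and for CHW and puts all of d on cohort. Comparing AD and AD+CHW with Cohort 1 TAU, and CHW with Cohort 2 TAU, also removes d, because each contrast then lies within one cohort.

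**Limits.** The multipliers are on the risk-difference scale; the path models are logistic, so they show direction and relative size there, not the exact error in an indirect effect. Claims cover only participants with MassHealth, so the shares in the fill analysis may differ somewhat.

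**The case against.** The strongest reply is that the plan knows about cohort. It names cohort as a factor for the factorial analysis in three places, and the mediation paragraph follows one of them directly. That paragraph is a short summary that lists no covariates of any kind, so silence does not prove omission. This stands: the fair statement is that no cohort term is stated. It does not dispose of the point, because a reader following the text as written would fit the models without one.

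A second reply is that d is unknown and the size therefore hypothetical. That also stands. For abstinence, where Section VII.3 expects 3 to 5% under TAU, a cohort difference of 3 to 5 points would be large. For medication use and fills the documents give no rate against which to judge it.

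A third reply is that the claims file lists the prescribing provider, from which cohort might be inferred. But that field belongs to claims. Participants with no fill have no prescriber in the file, so the denominators could not be split.

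A reader might also go further and infer that the primary comparison, Hypothesis 1c and Aims 2 to 4 draw on Cohort 2 TAU participants. The documents do not support this. Sections II and VII.1 introduce the factorial analysis as the way to bring Cohort 2 in, and Section VII.1 ties the three-arm analysis to clinics with at least 3 smokers. The claims comparison of providers randomised to AD or TAU is also confined to Cohort 1, since only there were clinics randomised. The permissive wording in "This comparison can be kept entirely separate from the main analysis of AD vs AD+CHW vs TAU" is loose and worth tightening, but it is not evidence of contamination.

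**Conclusion.** The point holds for two analyses, mediation and four-arm fills. As written, both mix randomised contrasts with differences between cohorts. The larger exposure is CHW alone vs TAU, at about 0.81 points of error per point of cohort difference; AD vs TAU is off by about 0.19. These figures rest on the stated allocation ratios, on equal arms in Cohort 1 and on arm coding. The absolute size rests on d, which is assumed.

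A reader might instead headline AD against no AD, where Cohort 2 would form 155/(336.7 + 155) = 31.5% of the no-AD side. That needs assignment to be collapsed to AD or no AD, a coding that neither passage states.

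The affected analyses are secondary or exploratory, and the primary comparison is not shown to be affected. The point is still more than missing detail: without a cohort field in the linkage data, the fill comparison cannot be repaired later. One limit remains even after adjustment. CHW without AD occurs only in Cohort 2, so an AD-by-CHW interaction cannot be told apart from a CHW effect that differs by cohort.

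**What to change.** - **Section VII.1, mediation.** Add cohort to both the mediator model and the outcome model. The text is in the past tense, so re-run the analysis if it was done without cohort.
- **Section VII.2, fills.** Compare AD and AD+CHW with Cohort 1 TAU, and CHW with Cohort 2 TAU, or adjust the four-arm comparison for cohort.
- **Section IV, claims linkage.** Add a cohort flag to the limited study data sent to MassHealth. An arm variable that splits TAU by cohort would serve equally well, since the other arms already identify their cohort.
- **Section VII.1, wording only.** Where the Cohort 2 comparison is said to be separable from the main analysis, replace the permissive verb (can) with a binding one (will).

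The cost is one extra data field, one model term and a small re-analysis. If the linkage has already been run, the file would have to be reissued with the flag. The plan's minimum cell size of 10 should be checked for Cohort 2 TAU (about 78 people) when it is crossed with demographics. Restricting the AD contrasts to Cohort 1 TAU leaves those 78 out, but they carry no randomised information about AD.

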The analysis of claims data on prescribing and use of smoking cessation medication treatment would not be possible if consent was required of all participants for access to their doctor's de-identified prescribing data. The study has enrolled 1166 participants. It is important to be able to utilize de-identified prescribing data for as many participants as possible in order to compare administrative measures (i.e., not based on self-report) of medication use across the study intervention arms to assess the effectiveness of the interventions on prescribing and the effects of medication use in this understudied population on abstinence. The funder specifically asked for these data to be included in the study, but made the request after the initial protocol was already implemented. The majority of withdrawn participants have lost agency services and would be extremely difficult to locate for consenting purposes. For participants we are able to contact, requiring consent to obtain and use de-identified pharmacy data would impose a significant participant burden. It would take approximately 30 minutes, a substantial amount of time, to explain the processes for disclosing and deidentifying the data and why this represents minimal risk.

4) Participants will be provided with additional pertinent information after participation.

At the initial meeting with the study coordinator, during the verbal consent process, participants will be provided with a fact-sheet that details important information about the study, including who can be contacted for more information. Participants will also be offered a copy of the Privacy Notice.

5) The research involves no more than minimal risk to the privacy of the participants.

This research involves no more than minimal risk to the privacy of participants. No PHI will be collected by MGH study staff. Please see above for the plan to protect identifying information from improper use and disclosure.

The use of pharmacy data involves no more than minimal risk to participants. All PHI disclosed to MassHealth will be protected using secure transfer and storage and we will disclose the minimum amount of data necessary (e.g., IDs, intervention date windows, age groups) that pose minimal risk to participants. No PHI will be included in any of the data files received from MassHealth or analyzed by MGH staff and the de-identified data will be protected (details above).

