- If behavioral smoking cessation support was recommended, we will ask if this support was used and, if so, what type (quit line, smoking cessation group or individual treatment) and how many sessions were attended.
- 2.4 If smoking: ***The Heaviness of Smoking Index*** (HSI) will be administered. It consists of 2 questions: time to first cigarette of the day and number of cigarettes smoked per day. The HSI and its individual items are strong predictors of quitting behavior, now validated in the International Tobacco Control cohort with 8,000 respondents/wave and 6,000 for prediction of cessation outcomes [75].
- 2.5 ***Health related quality of life***: The single item self-reported general health status question (SF-1) is well validated as a descriptor of individual health and wellbeing as well as community health status. [76] SF-1 scores are highly correlated with measures such as future health care use, mortality, disability, and mental health status [77-82] and SF-1 scores are significant indicators of health outcomes, independent of gender or racial/ethnic group. [78]
- 2.6 In those who report having quit smoking: Carbon monoxide in expired air, ***Expired CO***, will be measured with a small, hand-held CO monitor. To do so, participants will blow into a straw attached to the device, a Bedfont Smokerlyzer II (Kent, England), following a 15-second breath hold to verify self-report of non-smoking status. Expired CO <5 parts per million (ppm) is consistent with smoking abstinence.
 - We will measure cotinine in saliva in those whose expired CO is >5 ppm but report smoking zero cigarettes per day in the past 7 days and are not using nicotine replacement therapy. To do this, participants will provide a saliva sample via passive drool that will be tested with a NicAlert® dipstick (Nymox Corp., Hasbrouck Heights, NJ). The NicAlert® test displays seven zones that represent a range of cotinine levels from 0 (0–10 ng/ml) to 6 (> 1000 ng/ml). Participants that obtain a level between 1 (10–30 ng/ml) and 6 will be considered to be smoking

This is standard for biochemically verified abstinence and a critical component to obtaining reliable estimates of smoking status, the study's primary outcome, which will be used to judge the utility of the interventions being tested.

3. Interventions

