As part of their ongoing care, staff in CBFS and ACT psychiatric rehabilitation programs identify those in their programs who regularly smoke tobacco and the clinics providing their medical care. In cohort 1, clinics were randomized to receive AD to their clinicians or TAU. Participants whose primary care practices were assigned to receive AD were randomized to be offered a CHW (AD+CHW) or not (AD). In cohort 2, participants were randomized to receive CHW support or TAU. These interventions are detailed below.

There will be no prescription of or distribution of any smoking cessation medication of any kind to study participants by study staff. Any prescription of or recommendation for smoking cessation medication will be done in the clinical setting by clinical treaters.

3.1. Usual care (TAU) for adults with SMI in Massachusetts consists of rehabilitation services publicly funded by the state and traditional fee for service outpatient medical and psychiatric care. Importantly, medical care is not programmatically integrated with the psychiatric rehabilitation services. Patients who receive CBFS or ACT psychiatric rehabilitation

services from the primary agencies delivering such care in the Boston area, who agree to enroll in the study and whose primary medical clinic is assigned to the TAU arm of the study will meet with a RA at three consecutive, regularly-scheduled, annual psychiatric rehabilitation team meetings for brief survey. They will receive no other study-related intervention.

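### The mediation plan names no mediator–outcome confounder and no sensitivity analysis, so the medication-to-abstinence path, and the indirect and unmediated effects built on it, are open to confounding in either direction

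*Combined protocol and SAP*

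**What the plan says.** The mediation analysis is described only in Section VII.1 (Analytic Plan). Its stated purpose includes finding "the impact of TUD medication use and varenicline use specifically on abstinence we conducted mediation analyses using the combined cohorts". The model is given in one sentence: "We assessed associations between intervention assignment, TUD medication use, and year-2 abstinence via path analyses based on logistic regression". Any medication and varenicline are analysed separately, and "Estimates of the indirect effect were computed per each imputation run and pooled using Rubin's method". No covariate, identifying assumption or sensitivity analysis is named. Cohort appears as a factor only in the separate factorial analysis. The claims-data rationale in Section IV (waiver request, item 3) has a similar aim, to assess "the effects of medication use in this understudied population on abstinence".

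The mediator is not assigned by the study. Section III says that "the patient and their prescriber will decide together on the timing of initiation of any pharmacotherapeutic cessation aid", and Section V.3 says "There will be no prescription of or distribution of any smoking cessation medication of any kind to study participants by study staff".

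Baseline predictors are available. Sections V.2.1 to V.2.5 and the Time and Events Table show that demographics, living situation, past-year cessation services, the Heaviness of Smoking Index (HSI) and SF-1 are collected at Year 1. Section V.2.4 says of the HSI: "The HSI and its individual items are strong predictors of quitting behavior".

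**The concern.** Randomisation protects the path from assignment to medication use, and it protects the total effect of assignment. It does not protect the path from medication use to abstinence. Anything that makes a participant both more likely to take medication and more (or less) likely to be abstinent is counted as a medication effect and then carried into the indirect effect. The unmediated effect is distorted as well, because it is what remains after the indirect part is removed.

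The protocol implies such a factor. Section VII.4 builds the AD+CHW abstinence rate from the share who attempt to quit and their success, and people attempting to quit are plausibly those who take medication. At stake is the conclusion on how much of the intervention works through medication, and varenicline in particular.

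**Working it through.** **1. The plan's own figure.** The mediation analysis states no number. The nearest is the 15% AD+CHW abstinence rate in Section VII.4, built from 65% attempting, 30% of those succeeding and about 20% relapsing: 0.65 × 0.30 × (1 − 0.20) = 0.156, or 15.6% against the stated 15%. So sustained abstinence among attempters is 0.30 × 0.80 = 24%.

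**2. Baseline motivation as the confounder.** All inputs here are assumptions: half the sample is motivated, abstinence depends on motivation only, and medication has no effect. Write m1, m0 for medication use and y1, y0 for abstinence in motivated and unmotivated participants.

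P(abstinent | medication) = (m1·y1 + m0·y0)/(m1 + m0)

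P(abstinent | none) = [(1 − m1)·y1 + (1 − m0)·y0]/(2 − m1 − m0)

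The spurious indirect effect is the risk difference times an assumed 20-point rise in medication use.

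| m1, m0 | y1, y0 | Abstinent: medication vs none | Risk difference | Odds ratio | Spurious indirect effect |
|---|---|---|---|---|---|
| 35%, 10% | 14%, 4% | 0.118 vs 0.082 | 0.036 | 1.50 | 0.7 points |
| 50%, 8% | 20%, 3% | 0.177 vs 0.090 | 0.087 | 2.17 | 1.7 points |
| 40%, 15% | 12%, 6% | 0.104 vs 0.085 | 0.019 | 1.25 | 0.4 points |

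**3. Quit attempt as the confounder, using the protocol's figures.**

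- From Section VII.4: 65% attempt in AD+CHW; 24% sustained abstinence among attempters; 5% abstinence in TAU.
- Assumed: TAU attempt rate 0.05/0.24 = 20.8%; 0.1% abstinence among non-attempters; medication use 30–70% among attempters and 2–30% among non-attempters; equal arm sizes; no medication effect.
- Method: exact population-level logistic regression of abstinence on arm and medication. Indirect effect = [fitted P(abstinent | AD+CHW, medication) − fitted P(abstinent | AD+CHW, none)] × [P(medication | AD+CHW) − P(medication | TAU)].

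Worked case, 50% use among attempters and 10% among others:

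- P(medication | AD+CHW) = 0.65 × 0.50 + 0.35 × 0.10 = 0.360
- P(medication | TAU) = 0.208 × 0.50 + 0.792 × 0.10 = 0.183
- Fitted odds ratio for medication 2.50; fitted abstinence in AD+CHW 0.238 vs 0.111
- Spurious indirect effect (0.238 − 0.111) × (0.360 − 0.183) = 0.022, or 2.2 points
- Total effect 15.6% − 5.1% = 10.6 points before rounding, so the spurious share is 21%

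Over the full grid the odds ratio runs from 1.0 to 5.0 and the spurious indirect effect from 0 to 5.9 points (0 to 56% of the total). It is zero only where attempters and non-attempters use medication equally (30% and 30%). With attempt in the model, the odds ratio is 1.00 in every case.

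**4. The reverse direction.** Assume half the sample is heavily dependent, with medication use of 35% (control) and 60% (intervention) against 15% and 30% in the rest, and abstinence of 5% against 15%. With no medication effect, the fitted odds ratio is 0.72 and the indirect effect −0.6 points. With a true odds ratio of 2.0, the same set-up returns 1.40.

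**The case against.** Five points can be made on the other side.

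- **Silence is not proof.** The paragraph is a short summary, partly in the past tense. A reader might infer that the analysis demonstrably adjusted for nothing. The documents support only that no covariate is named. This stands. But Aim 2 lists its covariates, and an analyst following the mediation text as written would include none.
- **Direction.** A reader might infer that mediation through medication must be overstated. Nothing in the documents says that less dependent participants take more medication, and step 4 shows that the bias can run downward. This stands.
- **Baseline covariates are only proxies.** The listed survey items include no motivation or quit-attempt measure for current smokers, although the table's smoking questionnaire is not itemised. Section VII.2 (Exploratory Aim 3) expects the CHW to encourage attempts, so attempting is partly a result of assignment. Baseline adjustment cannot remove that. This stands, and it is why a sensitivity analysis is needed as well.
- **The wording is already cautious.** The model sentence speaks of associations. The same paragraph also speaks of impact, so this is met only in part.
- **Limited consequence.** Mediation is not a listed hypothesis in Section II, and mechanism work under Aim 3 is exploratory. A reader might infer that the trial's main result is in doubt. It is not: the AD+CHW versus TAU comparison does not use the mediator.

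**Conclusion.** The point holds as a gap in the specification that has a better and nearly free alternative. As written, the medication-to-abstinence path and the indirect and unmediated effects are open to confounding by non-randomised medication use. The bias is upward if people trying to quit take more medication. It could be downward if heavier smokers take more and quit less.

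The documents contain no mediation result and no medication-use rates, so the size cannot be fixed. The 0 to 5.9 points under the quit-attempt model, and the 0.4 to 1.7 points under baseline motivation, illustrate the possible scale under the stated assumptions; they are not estimates for this trial. Randomised total effects and the primary comparison are untouched.

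**What to change.** In both the mediator and the outcome model, include cohort and these Year 1 variables: HSI, past-year cessation medication use and advice, age, sex, race, living situation and SF-1. Cohort belongs there because the pooled cohorts had different arms and allocation, so assignment is randomised only within cohort.

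Define the mediator as self-reported use in the study database. The de-identified claims file described in Section IV carries no HSI, SF-1 or living situation and cannot be linked back to the study ID.

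Do not simply add post-randomisation quit attempts as a covariate. The CHW is expected to change them, so ordinary adjustment would not identify the indirect effect.

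Because baseline adjustment is only partial, state the no-unmeasured-confounding assumption and report the confounder strength that would bring the indirect effect to zero. Describe the medication-to-abstinence path as an observational association throughout.

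The cost is plan wording and a few model terms, plus a re-fit within each imputation if the analysis has already been run. No new data are needed. Indirect effects may change and would be reported with more caution.
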